3.5. Exploratory Objectives

3.6. Brief Description

This is an international, Phase 3 randomized, double-blind, placebo-controlled with active control (tolterodine), parallel-group, multicenter study in men and women with OAB, to be conducted in conformance with ICH GCP. The study will assess the safety, tolerability, and efficacy of 75 mg vibegron versus placebo. Patients will be randomized 5:5:4 in a double-blind fashion to one of three treatment arms: vibegron 75 mg, placebo, or tolterodine ER 4 mg, all administered once daily for 12 weeks during the Treatment Period.

Patient participation in the study will be up to 17 weeks post randomization (including authorized windows). This study consists of a Screening Period (1 to 5 weeks), a single-blind Run-in Period (2 weeks), a randomized double-blind Treatment Period (12 weeks) and a Safety Follow-up Period (4 weeks). All patients who complete the Week 12 Visit may be offered the opportunity to enroll in a 40-week double-blind extension study RVT-901-3004 (which will be conducted under a separate protocol), until enrollment in that study is complete. Patients who do not enroll into the optional extension study will

have a Follow-up Visit approximately 28 days after the patient's last dose of Study Treatment (i.e., at Week 16 for patients who complete the Week 12 Visit, or approximately 4 weeks after withdrawal for patients who discontinue the study early). Additionally, Unscheduled Visit(s) may be arranged for patients with study-related safety concerns as needed.

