3.11. Study Procedures and Flowchart

This study consists of a Screening Period (1 to 5 weeks), a single-blind Run-in Period (2 weeks), a randomized double-blind Treatment Period (12 weeks) and a Safety Follow-up Period (4 weeks). The schedule of activities is given in [Table 3.11.1](#).

Table 3.11.1: Schedule of Activities

Study Period:	Screening/ Washout	Run-in	Treatment					Safety Follow-up/ Unscheduled	
Visit Number:	Visit #1	Visit #2	Visit #3	Diary Only	Visit #4	Visit #5	Visit #6	UNS #	Visit #7
Visit Name:	Screening ¹	Run-in	Baseline	Week 2	Week 4	Week 8	Week 12 or Early WD	Unsch- eduled ²⁵	Follow- up ²⁶
Study Day:	-49 to -15	-14	1	15	29	57	85 or Early WD		113 or Early WD + 28
Permitted Visit Window:		± 3 Days			± 3 Days	± 3 Days	± 3 Days		± 3 Days
Informed Consent	X								
Inclusion/Exclusion Criteria Eligibility Review	X	X	X						
Medical and Medication History	X	X	X						
Electronic Diary (eDiary) ² :									
eDiary Device:									
Device Setup/Function Check ³	X	X	X		X	X	X	X	
Device Training/Re-Training ⁴	X	X	X		X	X		X	
Dispense/Collect eDiary Device	X						X		
Patient Voiding Diary:									
Patient Voiding Diary Training/Re-Training ⁵	X	X	X		X	X		X	
Patient Completes Patient Voiding Diary ⁶	X	X		X	X	X	X		
Urine Volume Diary:									
Urine Volume Diary Training/Re-Training ⁵	X	X	X		X	X		X	
Dispense Urine Collection/Measurement Supplies	X								
Patient Completes Urine Volume Diary ⁷	X	X		X	X	X	X		
Diary and Visit Reminders									
Phone Calls / Optional SMS reminders ⁸	X	X		X	X	X	X		

Study Period:	Screening/ Washout	Run-in	Treatment					Safety Follow-up/ Unscheduled	
Visit Number:	Visit #1	Visit #2	Visit #3	Diary Only	Visit #4	Visit #5	Visit #6	UNS #	Visit #7
Visit Name:	Screening ¹	Run-in	Baseline	Week 2	Week 4	Week 8	Week 12 or Early WD	Unsch- eduled ²⁵	Follow- up ²⁶
Study Day:	-49 to -15	-14	1	15	29	57	85 or Early WD		113 or Early WD + 28
Permitted Visit Window:		± 3 Days			± 3 Days	± 3 Days	± 3 Days		± 3 Days
Patient Reported Outcomes ⁹ :									
Global Impression Items (PGI-Severity, PGI-Control, PGI-Frequency, PGI-Leakage, and PGI-Change)			X		X	X	X		
Overactive Bladder Questionnaire (OAB-q LF)			X				X		
Work Productivity and Activity Impairment Questionnaire-Urinary Symptoms (WPAI-US)			X				X		
EQ-5D			X				X		
Post-Void Residual (PVR) Volume ¹⁰		X					X		
Physical Exam ¹¹	X	X						X	X
ECG ¹²	X							X	
Vital Signs ¹³	X	X	X		X	X	X	X	X
Adverse Events ¹⁴	←=====→								
Serious Adverse Events ¹⁵	←=====→								

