Concomitant Medication Review ¹⁶	←=====→								
Clinical Laboratory Assessments:									
Chemistry	X		X		X		X	X	X
Hematology	X		X		X		X	X	X
Urinalysis Dipstick ^{17,18}	X		X		X		X	X	X
Urine Pregnancy β-hCG (women) ¹⁹	X	X	X		X	X	X	X	X
IxRS Randomization to Study Treatment			X						
Dispense Study Treatment ²⁰		X	X		X	X		X	

Study Period:	Screening/ Washout	Run-in	Treatment					Safety Follow-up/ Unscheduled	
Visit Number:	Visit #1	Visit #2	Visit #3	Diary Only	Visit #4	Visit #5	Visit #6	UNS #	Visit #7
Visit Name:	Screening ¹	Run-in	Baseline	Week 2	Week 4	Week 8	Week 12 or Early WD	Unsch- eduled ²⁵	Follow- up ²⁶
Study Day:	-49 to -15	-14	1	15	29	57	85 or Early WD		113 or Early WD + 28
Permitted Visit Window:		± 3 Days			± 3 Days	± 3 Days	± 3 Days		± 3 Days
Study Treatment Return/Accountability Review ²¹			X		X	X	X		
Administer Witnessed Dose of Study Treatment ²²		X	X						
Pharmacokinetic Sampling (PK Subset Only):									
PK Sample Collection ²³					X	X	X		
Collect Date/Time of Prior Dose ²⁴					X	X	X		

Abbreviations: IxRS, interactive voice or web response system, PK, pharmacokinetic; WD, withdrawal; β-hCG, β-human chorionic gonadotropin

Table Footnotes:

Screening

1. The time between the Screening and Run-in Visits may be up to 5 weeks, to allow for washout of prior OAB medications (if needed) and completion of the Patient Voiding Diary and Urine Volume Diary.

Electronic Diary (eDiary)

2. The Electronic Diary (eDiary) for this study includes both the Patient Voiding Diary and the Urine Volume Diary, and will be implemented via an eDiary device (provisioned smartphone). A paper diary will be provided to all patients to be used as a back-up when necessary. If a back-up paper diary is used, it should be collected at each study visit.

eDiary Device

3. At Screening, site personnel will setup the eDiary Device, confirm proper functioning, and dispense the eDiary Device to the patient. At each subsequent visit during the Treatment Period, site personnel will confirm that the eDiary Device is functioning properly.

4. Specific training on device operation will be provided to the patient at Screening, with re-training provided at each subsequent visit.

Patient Voiding Diary and Urine Volume Diary

5. Specific training on completion of the Patient Voiding Diary and Urine Volume Diary will be provided to the patient at Screening, with re-training provided at each subsequent visit.

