6.5. Visit Windows

Visit windows will be assigned based on the analysis need and the type of data. There are two types of data to be assigned an analysis visit: diary data and non-diary data.

Visit Windowing for Diary Data:

For diary data (micturitions, UUI, urgency episodes, total incontinence etc.), where the assessment has been performed at a specific visit (for example confirmation of completion of diary) the assessment will be analyzed at the scheduled visit entered. For diary data whereby only a date/time is given, the record will be assigned based on the dates of the scheduled visits performed. For example, if Run-in visit occurs on 01SEP2018 and Baseline visit occurs on 14SEP2018, any diary data occurring after 01SEP2018 up to and including the day before Baseline visit (13SEP2018) will be windowed for the analysis as “Baseline”. This applies for all analysis visits except for Week 2 and Week 4 as there is no Week 2 scheduled visit; in this instance, Week 2 and Week 4 will be assigned based on the assessment being windowed as Week 4 per the above rule, and then the following windowing based on analysis day (relative to first date of double-blind medication) will be applied:

- Date of diary assessment after scheduled Baseline visit from Analysis Day 6 up to and including Analysis Day 22: Assigned as Week 2;
- Date of diary assessment on or after Analysis Day 23 up to and including the day before the scheduled Week 4 visit: Assigned as Week 4.

For diary data, with the exception of week 12 only the latest 10 complete diary day observations leading up to any scheduled visit will be included in the analysis of the diary. For week 12, the diary within the latest 10 complete diary day observation will be included if available. If not then the complete diary day observation within the latest 14 days will be included. For both scenarios, there must be 4 or more complete diary days available for the period to be analyzed. Otherwise, if there are less than 4 complete diary days available, the period will be set to missing for the analysis.

Visit Windowing for Non-Diary Data:

For any non-diary data involving two scheduled visits (OAB-q-LF, WPAI-US, EQ-5D, Physical Exam and ECG), the analysis visit will be assigned as the scheduled visit performed in the eCRF. For all other non-diary data, analysis visit will be windowed using the rules given in [Table 6.5.1](#) below. These adjusted analysis-defined windows will be

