based on the collection schedule listed in the protocol and variables will be windowed to the closest scheduled visit for that variable.

There is no analysis window for the Screening, Run-in, or Baseline visit; those will be analyzed as collected. Post-baseline visits will be windowed based on the target day of the analysis window, which is relative to Day 1 (the first day of double-blind medication).

Table 6.5.1: Analysis Window

Visit Name	Nominal Visit	Target Day	Analysis Window
Screening	Visit 1	-49 to -15	N/A
Run-in	Visit 2	-14	N/A
Baseline	Visit 3	1	N/A
Week 4	Visit 5	29	[2, 42]
Week 8	Visit 6	57	[43, 70]
Week 12	Visit 7	85	[71, 98]
Follow-up	Visit 8	113	[99, ∞)

If a patient has multiple values of the same measure in an analysis window, then the value collected closest to the target day will be used. If the visits are equidistant from the nominal day, then the later visit will be used. All values will be stored in analysis datasets.

A laboratory result based on an inadequate sample will not be used in the presentation of sample statistics if a repeat sample was drawn to replace the sample, but the inadequate sample will be listed.

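### Day-only visit windows place an early withdrawal's off-treatment Follow-up vital signs and labs in the Week 4, 8 or 12 rows of the safety tables

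*SAP*

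**What the plan says.** SAP Section 6.5 assigns five non-diary measures (OAB-q LF, WPAI-US, EQ-5D, physical examination, ECG) by the visit recorded in the eCRF. For the rest, "For all other non-diary data, analysis visit will be windowed using the rules given in" Table 6.5.1. The basis is study day: "Post-baseline visits will be windowed based on the target day of the analysis window, which is relative to Day 1". The windows are Week 4 [2, 42], Week 8 [43, 70], Week 12 [71, 98] and Follow-up from Day 99. Only Screening, Run-in and Baseline have no window.

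The section adds that "variables will be windowed to the closest scheduled visit for that variable". When several values share a window, "the value collected closest to the target day will be used". For ties, "If the visits are equidistant from the nominal day, then the later visit will be used".

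Section 3.6 places Follow-up "approximately 4 weeks after withdrawal for patients who discontinue the study early", and Table 3.11.1 gives its day as "113 or Early WD + 28". Vital signs, chemistry and hematology are all collected at Follow-up. Under "Clinical Laboratory Assessments", chemistry and hematology have no scheduled Week 8 draw. Footnote 26 to that table has the Week 12 procedures done at withdrawal, so a withdrawal-visit value normally exists as well.

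Sections 9.4 and 9.5 summarize labs and vital signs by visit. Neither restricts the rows to values on treatment or sets Follow-up records aside.

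**The concern.** The windows assume that Follow-up happens near Day 113. That holds for patients who complete Week 12, but an early withdrawal's Follow-up moves with the withdrawal date. A patient who withdraws on Day 50 attends Follow-up on about Day 78, and Table 6.5.1 calls that Week 12. No sentence exempts the record.

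The by-visit means, changes from baseline, out-of-range lab counts and by-visit lab shift tables would then show values taken about four weeks after withdrawal under visits that the Schedule places in the Treatment period. In some cases the withdrawal-visit value is dropped from the row in favour of the later one. Collecting these data is not at issue, since the SAP follows safety to 28 days after the last dose. The error is in the label.

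**Working it through.** **Reproducing Table 6.5.1.** Target days are 29, 57, 85 and 113. The midpoints are (29+57)/2 = 43, (57+85)/2 = 71 and (85+113)/2 = 99. Giving each midpoint to the later visit yields exactly the printed windows.

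**Inputs.** From the SAP: 500 patients per arm and 10% dropout (Section 3.8), so 50 withdrawals; Follow-up on day d + 28 for withdrawal on day d. Assumed, because the SAP is silent: withdrawals evenly spread over d = 2 to 84 (83 days, 50/83 = 0.602 per day), every withdrawal attends Follow-up, and earlier scheduled visits fall on target.

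**Vital signs**

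| Withdrawal day | Follow-up day | Row assigned | Values (days × 50/83) | Share of row |
|---|---|---|---|---|
| 2–14 | 30–42 | Week 4 | 13 days, 7.8 | 7.8/500.0 = 1.57% |
| 15–42 | 43–70 | Week 8 | 28 days, 16.9 | 16.9/492.2 = 3.43% |
| 43–70 | 71–98 | Week 12 | 28 days, 16.9 | 16.9/475.3 = 3.55% |
| 71–84 | 99–112 | Follow-up (correct) | – | – |

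Row denominators are 500 less those who withdrew too early to have any value in the row: 500 − 7.8 = 492.2 and 500 − 41 × 50/83 = 475.3. The total mislabelled is 69 × 50/83 = 41.6.

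For d = 2–14 the withdrawal-visit value shares the Week 4 window. It lies 29 − d = 15 to 27 days from target, and the Follow-up value d − 1 = 1 to 13 days. Follow-up is selected, so 7.8 withdrawal-visit values are displaced.

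**Chemistry and hematology.** Section 6.5 can be read two ways.

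(a) *The closest scheduled visit for the variable governs.* With no Week 8 draw the midpoint is (29+85)/2 = 57, giving Week 4 [2, 56] and Week 12 [57, 98].
- d = 2–28: Follow-up is labelled Week 4. It is selected when d − 1 ≤ 29 − d, that is d ≤ 15 (a tie at 15 goes to the later value). This gives 14 days, 8.4 values, 1.69% of 500.
- d = 29–70: Follow-up is labelled Week 12 and selected. This gives 42 days, 25.3 of 483.7 (500 − 27 × 50/83), or 5.23%.
- Total 56 × 50/83 = 33.7. Displaced: d = 2–15 and 57–70, 28 days, 16.9.

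(b) *The printed windows govern.*
- Week 4 for d = 2–14 (7.8, 1.57%) and Week 12 for d = 43–70 (16.9 of 475.3, 3.55%). Total 41 × 50/83 = 24.7; displaced 7.8.
- In addition, 16.9 Follow-up labs (d = 15–42) and 16.9 withdrawal-visit labs (d = 43–70) are labelled Week 8, where no draw is scheduled.

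**Sensitivity** (per 500-patient arm; vital signs / labs a / labs b)

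| Scenario | Mislabelled | Displaced |
|---|---|---|
| Gap 28, even timing | 41.6 / 33.7 / 24.7 | 7.8 / 16.9 / 7.8 |
| Gap 25 | 41.6 / 33.7 / 25.3 | 11.4 / 18.7 / 10.2 |
| Gap 31 | 39.8 / 32.5 / 22.9 | 6.0 / 13.9 / 6.0 |
| Earlier timing (weight 85 − d) | 48.5 / 36.7 / 25.8 | 14.4 / 19.7 / 14.4 |
| Later timing (weight d − 1) | 34.6 / 30.7 / 23.6 | 1.3 / 14.1 / 1.3 |
| All on Days 71–84, gap 28 | 0 | 0 |

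Half attendance at Follow-up halves every count.

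**Effect on a mean.** If a drug effect vanished completely off drug, an assumed 2 mmHg difference at Week 12 would read 2 × (1 − 0.0355) = 1.93.

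**The case against.** The day ranges are not in dispute; the objections concern weight and scope.

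- *Windowing by elapsed time is a disclosed convention, applied alike to all arms, and the SAP never calls these rows on-treatment.* True as far as it goes. But the Schedule places Weeks 4, 8 and 12 under Treatment and gives Follow-up a period of its own, so a reader will take the rows as on-treatment.
- *Reading (b) for labs ignores the closest-scheduled-visit sentence.* Reading (a) is the more natural one. Still, the same section sends these data to a table with a printed Week 8 window, and mislabelling arises under either reading. Printing lab windows only makes the existing rule explicit.
- *The size depends on assumptions and is small.* This stands. The SAP gives neither the timing of withdrawal nor attendance at Follow-up, no safety testing is planned, and all values are stored and listed. The shift tables to maximum, minimum and last value do not depend on the labels.
- *A rule for unscheduled values goes beyond the defect, and a cut-off at the Early WD visit is undefined for a patient who never had one.* Also fair. The sentence that keeps the Follow-up label cures the main problem by itself; the rest is tidying.

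**Conclusion.** The concern holds, as a minor point. As written, Section 6.5 and Table 6.5.1 put the Follow-up vital signs of patients who withdraw on Days 2–70 into the Week 4, 8 or 12 rows, and their Follow-up labs, for most of those days, into Week 4 or 12. Completers and patients who withdraw from Day 71 on are labelled correctly (28-day gap).

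Under the even-timing illustration this is about 42 vital-sign values per 500-patient arm, with 8 withdrawal-visit values displaced. For each lab test it is 25 to 34 values, with 8 to 17 displaced. These counts are not bounds: they rest on 10% dropout, the assumed timing and full attendance, and could be zero if all withdrawals came late.

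Diary and questionnaire efficacy results, adverse event counts and listings are unaffected. A safety conclusion is unlikely to change, but the by-visit tables would not show what their row labels say.

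**What to change.** Add to SAP Section 6.5:

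> Records from the visit named Follow-up in the eCRF are always assigned to Follow-up, regardless of study day. The Week 4, 8 and 12 windows and the closest-to-target rule use only values collected up to and including the Week 12/Early WD visit. Unscheduled values after that visit get no analysis visit; they are listed and still count in the shift tables to maximum, minimum and last value.

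For a patient with no Early WD visit, the cut-off in the second sentence could be the last treatment-period visit attended. Also print separate chemistry and hematology windows: Week 4 [2, 56] and Week 12 [57, 98], with Follow-up by visit name.

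The cost is a few sentences, one line of lab windows and a visit-name condition in the dataset programs. Section 6.5 already uses the eCRF visit for physical examination and other measures. The Week 4, 8 and 12 rows will hold slightly fewer values. The change should be made before unblinding.

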6.6. Pooling of Centers

No investigation of center effects is planned; data from all centers will be pooled.

6.7. Subgroups

To determine whether the treatment effect is consistent across various subgroups, the co-primary endpoints will be summarized descriptively for each of the following subgroups:

- Region (US vs. Non-US)
- Age category 1 (<40, ≥40 to <55, ≥55 to <65, ≥65 to < 75, ≥75 years)
- Age category 2 (<65, ≥65 years)
- Age category 3 (<65, ≥65 to < 85, ≥85 years)
- Race (white vs. other)
- Sex (female vs. male)
- Males with BPH vs. males without BPH
- Prior anticholinergic use in the last 12 months (yes vs. no)

- Prior beta-3 agonist use in the last 12 months (yes vs. no)
- OAB Type (OAB Wet vs. OAB Dry)
- OAB-d Type (OAB Wet vs. OAB Dry)

The details of the analysis of subgroups used for statistical inference of the co-primary endpoints are given in [Section 8.1.4](#).

A list of anticholinergics is given in the protocol in Table 4 of Section 7.9.3.

7. DEMOGRAPHIC, OTHER BASELINE CHARACTERISTICS AND MEDICATION

7.1. Patient Disposition and Withdrawals

Patient disposition will be summarized by treatment arm for the Screened, Run-in and Randomized Sets separately. The summary table will show the frequency and percentage of patients in each of the analysis sets and those who discontinued the study prematurely along with the primary reasons for discontinuation. For the summary under the Randomized Set, additionally the number of patients dispensed and took at least one dose of study medication, plus the number of patients completed study are also summarized.

The frequency and percentage of patients with at least one major Protocol Deviation (PD), major PD by classification and reasons/category for PD will be summarized by treatment arm for the FAS. Inclusion in each of the analysis sets (SAF, FAS, FAS-I, PPS, PPS-I, and PKS), and any reasons for exclusion will be summarized by treatment arm for the Randomized Set. Both will be listed also for the FAS and Randomized Sets, respectively.

Screen Failure, Run-in and Double-Blind Period disposition, with reasons for discontinuation of study will also be listed, including the date of discontinuation.

Eligibility criteria, screening failures (including date and primary reason for failure), and informed consent (protocol version, informed consent version date and date signed) will be listed for all patients screened.

A summary of randomized patients by country and investigator will be provided.

Randomization details will also be listed, including the date of randomization, randomization number and randomization strata (OAB Wet/Dry and Sex), and OAB-d Type (Wet/Dry).

7.2. Demographic Characteristics

All demographic and baseline characteristic data will be summarized by treatment group using descriptive statistics for all patients for each of the following analysis sets: SAF, FAS, FAS-I, PPS and PPS-I.

Sex, Region (US and non-US), OAB Type (OAB Wet and OAB Dry), OAB-d Type (OAB Wet, OAB Dry and Missing), Prior Anticholinergic Use in the Last 12 Months (Yes/No), Prior Beta-3 agonist Use in the Last 12 Months (Yes/No), Benign Prostatic Hyperplasia (BPH) (males only: Yes/No), Diabetes Mellitus (Yes/No), Baseline Hypertension (Yes/No), Pre-existing Hypertension (Yes/No), Child-bearing Potential (females only: Yes/No), Age category 1 (<40, ≥40 to <55, ≥55 to <65, ≥65 to <75, ≥75 years), Age

category 2 (<65, ≥65 years), Age category 3 (18 to <65, ≥65 to <85 years, ≥85 years), Ethnicity and Race (white and other) will be summarized by the number and percentage of patients in each category.

Prior Anticholinergic Use in the Last 12 Months and Prior Beta-3 agonist Use in the Last 12 Months are considered prior medications and will be defined as medications documented on the Prior and Concomitant Medications eCRF as having stopped prior to the Run-in Visit.

Baseline Hypertension will be defined as baseline systolic blood pressure (SBP) ≥140 mmHg or baseline diastolic blood pressure (DBP) ≥90 mmHg, regardless of medical history.

Pre-existing hypertension will be defined as having a medical history of hypertension or Baseline hypertension (baseline SBP ≥140 mmHg or baseline DBP ≥90 mmHg).

Age (years), height (cm), weight (kg) and BMI captured at Screening will be summarized as a continuous variable.

Unless otherwise stated, percentages will be calculated out of the number of patients in the given Analysis Set.

All demographic data will be listed.

7.3. Medical History and Concomitant Diseases

Descriptions of medical history findings will be coded using Medical Dictionary for Regulatory Activities (MedDRA) version 20.0 or higher.

A disease or illness reported as medical history without a start date will be included in medical history without a date assigned.

Medical history will be sorted by descending overall frequency, by SOC and PT in the summary table. Medical history data listings will be sorted by treatment, patient number, start date, SOC and PT.

7.4. Other Baseline Characteristics

The data from the last complete voiding diary during run-in period (micturitions, urge incontinence episodes, urgency episodes, total incontinence episodes, and volume voided) prior to first dose of double-blind medication will be used as baseline for each patient. The daily averages for micturitions, urgency episodes, and urge urinary incontinence episodes will be calculated as the sum of the event type on complete diary days divided by the number of Complete Diary Days. These will be summarized by treatment group and

overall using descriptive statistics for continuous data for all patients in each analysis set SAF, FAS, FAS-I, PPS and PPS-I at baseline.

All data will be listed.

